### 3.2 Endpoints

In order to assess implementation and effectiveness of the cardiovascular CPR (targeted at GPs) on the management of chest pain and patient's outcome, we will measure:

- Hospitalizations, severe CHD at 9 months among patients included
- Number and type of extra investigations and referrals run by GPs to manage patient's chest pain
- Use/non use of the CPR by GPs, acceptability and satisfaction

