## Summary

This protocol details the phase IV study aiming to assess both impact and implementation of a new clinical prediction rule (CPR) only based on patient's history and physical examination in order to help general practitioners ruling out a cardiac origin to chest pain without further investigations. It is built upon the data of the TOPIC (Thoracic Pain In Community) study run in 2001 to measure occurrence and aetiologies of chest pain in primary care. Internal and external validation studies have been done by now. The current study is a prospective cohort cluster randomized trial with two arms: on one hand general practitioners aided by the CPR and on the other hand general practitioners working according to their usual clinical practice. The target population is patients consulting primary care settings and reporting any type of chest pain. We will measure the acceptability, satisfaction and use of the CPR by physicians and intend to show that it can spare useless extra investigations without compromising patients' management and outcome. To reach this goal, 300 general practitioners and 15,000 patients are needed. Inclusion and exclusion criteria are defined. The follow-up lasts 9 months and the main endpoints measured are hospitalizations, diagnostic of coronary artery disease, extra investigations and referrals run to determine the origin of chest pain. We will also assess use, acceptability of the CPR and satisfaction among the physicians selected to use it. An intermediate analysis is planned at 3 months and stopping rules are defined. A case report form has to be filled in for each patient with chest pain. No adverse events are expected. Independent reviewing and follow-up will insure correct management of the patients enrolled. The current protocol will be submitted to an ethical committee.

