## 2. Objectives

- To measure the acceptability, satisfaction and use of the CPR by GPs in primary care patients complaining of chest pain.
- To show that using the cardiovascular CPR as an assistive tool to rule out CHD in primary care practices can spare useless extra investigations, without compromising patient's management and outcome.

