## 6. Evaluation criteria

Aiming to assess both implementation of the cardiovascular CPR and its potential effect on chest pain management, evaluation criteria are split in two classes. On one hand, criteria concerning use of the CPR, evaluated by few questions in de CRF directly addressed to GPs. On the other hand, criteria aiming to measure impact of the CPR on chest pain management and patient's outcome. These are to be filled in by GPs for each patient complaining of chest pain at the time of the index visit (CRF) and at the end of follow-up (6 to 9 months), and by research team for intermediate analysis.

Implementation:	
Acceptability of the CPR	
 
- Use/non use of the CPR
 
- Reassurance with low-risk result
 

Satisfaction	
 
- Discrete visual analogue scale
 

Impact:	
Extra investigations of chest pain	
 
- None
 
- ECG
 
- Thoracic radiography
 
- Laboratory (CRP, FSC, CK, D-dimers, Troponines, BNP)
 
- Cardiac stress test
 
- Others (precise)
 

Referral	
 
- None
 
- Hospital / emergency setting
 
- Cardiologist (less than 6 hours, less than one week, more than one week, telephonic interview)
 
- New consultation
 
- Other (precise)
 

Patient's outcome at 9 months	
 
- Hospitalisation(s) during follow-up
 
- CHD / no CHD, with degree of certainty (discrete visual analogue scale)
 

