### 7.2 Documents storage and keeping

The documents collected during the current study are the CRF, questionnaires filled in by research team at 3 months and end of follow up questionnaires for each patient included. All the files regarding the current trial will be kept at the Institute of General Medicine, University of Lausanne, Switzerland.

GPs have to send index visit CRF to research team once a week, as well as end of follow up questionnaires (routine consultation 6 to 9 months after index visit or telephonic interview). Questionnaires for intermediate analysis at 3 months will be filled in by research team during a telephonic interview and kept in the research department.

A single code will be attributed to each patient and GP, so that complete anonymity is insured. Patients' details will be known only by their GP to insure maximal confidentiality. Each GP makes a ranking list of participating patients with name, code and phone number to assure the follow up. Furthermore, and only with patients' consent, mobile phone number is attached to identification code to allow the research team to contact patient in case of incomplete CRF. Mobile phone numbers will be deleted after intermediate analysis.

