## 10.3 Dropouts and missing data management

Every case of dropout will undergo a complete analysis to avoid any bias. In case of missing data, the following procedure will be attempted:

- 1) Complete missing data by contacting GP/patient if feasible
- 2) Extrapolation if feasible
- 3) Exclusion of patient

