### **Hospitalisations en lien avec la douleur thoracique durant la période de suivi :**

oui  / non

*Si oui*, durée : \_\_\_\_ jour(s)

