### **Diagnostic retenu pour la douleur thoracique :**

Maladie coronarienne : oui  / non

Degré de certitude : faible 0 - 1 - 2 - 3 - 4 fort

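### Severe CHD at 9 months cannot be derived from the follow-up form, and death has no field, so the safety comparison cannot be made as planned

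*Protocol*

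**What the plan says.** The second objective (section 2) is to show that the clinical prediction rule (CPR) "can spare useless extra investigations, without compromising patient's management and outcome". For patient outcome, section 3.2 lists "Hospitalizations, severe CHD at 9 months among patients included", and the synopsis repeats this.

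Other parts of the protocol describe the same outcome differently. The Summary says "the main endpoints measured are hospitalizations, diagnostic of coronary artery disease, extra investigations and referrals". Section 6 has hospitalisation during follow-up and "CHD / no CHD, with degree of certainty (discrete visual analogue scale" as its two patient outcomes at 9 months.

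The follow-up form in Annex 3 serves both 3 and 9 months and has two outcome items. "Hospitalisations en lien avec la douleur thoracique durant la période de suivi" takes yes/no and a number of days. "Diagnostic retenu pour la douleur thoracique" takes coronary disease yes/no and a certainty score from 0 to 4.

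At 3 months the research team completes the form by telephoning the patient (section 7.2). At 9 months the GP completes it, from a consultation or a telephone interview (sections 3.1 and 3.4). Section 10.3 handles missing data in three steps: retrieval from the GP or patient, extrapolation, and finally "Exclusion of patient".

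**The concern.** The trial gives GPs a tool meant to spare investigations. The safety question is whether patients labelled low risk come to harm that further investigation might have prevented. The outcomes that answer it are severe coronary events and death. The first is named as an endpoint but has no definition and no severity item on the form. The second appears nowhere.

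This is not a detail that a later analysis plan can settle, because it concerns data that will not have been collected. It also reaches the trial's own safeguard: sections 3.4 and 8.2 rely on the 3-month analysis to reveal an unfavourable effect and stop the study, and that analysis draws on interviews that a patient who has died cannot give.

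**Working it through.** **1. How the form would record different courses.** The outcome items printed in Annex 3 give:

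| Patient's course | Chest-pain hospitalisation | Coronary disease | What the data can show |
|---|---|---|---|
| Infarction, admitted, survived | yes | yes | CHD, ungraded |
| Stable CHD, admitted for work-up | yes | yes | same entry as the row above, apart from days |
| Stable CHD, not admitted | no | yes | CHD, ungraded |
| Fatal infarction diagnosed and known to the GP | yes or no | yes | CHD; the death is invisible |
| Death with no chest-pain admission and no CHD diagnosis | no | no, or no form returned | a good outcome, or missing |

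The certainty score measures confidence in the diagnosis, and length of stay is not a severity grade. Neither separates the first two rows. The last row is where a serious outcome can disappear.

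**2. How many patients this question concerns.** Illustration, assuming that the 12% CHD frequency in section 1.1 and the external-validation sensitivity of 85.6% in section 1.2 both apply here. Patients per arm: 150 × 50 = 7,500. CHD patients labelled low risk in the CPR arm: 7,500 × 0.12 × (1 − 0.856) ≈ 130.

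**3. What could happen if deaths are lost.** The protocol gives no death rate, so every mortality figure here is assumed. Let 8% of enrolled patients in each arm be hospitalised and alive at 9 months (section 10.1 gives 8%, 53/672, hospitalised up to 12 months). Let control mortality be d and CPR-arm mortality 1.5d, with every death excluded.

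- True difference in hospitalised or dead: 1.5d − d = 0.5d.
- Observed difference: 0.08/(1 − 1.5d) − 0.08/(1 − d).

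| d | Expected control deaths | True difference | Observed difference |
|---|---|---|---|
| 0.5% | 37.5 | 0.25 points | 0.02 points |
| 1% | 75 | 0.50 points | 0.04 points |
| 2% | 150 | 1.00 points | 0.08 points |

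This is the worst case. Deaths entered through the hospitalisation or CHD items would reduce the loss. With equal mortality in both arms, both differences are zero.

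**4. What could happen if missing patients are excluded.** Take a true rate p = 8% in both arms, a fraction q missing, and risk r × p among the missing. The observed rate is p(1 − qr)/(1 − q).

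- q equal in both arms: observed difference zero, whatever r.
- q = 5% control, 10% CPR, r = 2: 0.08 × 0.90/0.95 = 7.58% against 0.08 × 0.80/0.90 = 7.11%, a gap of 0.47 points.
- Same q, r = 3: 0.08 × 0.85/0.95 = 7.16% against 0.08 × 0.70/0.90 = 6.22%, a gap of 0.94 points.

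Swapping q between the arms reverses the sign. For scale, with the protocol's coefficient of variation of 0.2, the 95% half-width for a difference at 8% is 1.96 × √{[2 × 0.08 × 0.92/50 + 2 × 0.2² × 0.08²]/150} = 0.94 points. The missing fractions and r are assumptions. At r = 3 the missing CPR patients carry a 24% risk against 6.22% in those observed, a ratio of 3.9, which is an extreme case.

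**The case against.** The strongest reply is that the loss is narrower than it looks, and much of that reply stands.

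- **Severe CHD drops out of the analysis.** A reader might infer this, but such a patient is entered as CHD, and as hospitalised if admitted for chest pain. What is lost is the grade.
- **Patients with missing outcomes are simply excluded.** Exclusion is the third step in section 10.3, after retrieval and extrapolation.
- **Retrieval is blocked at 9 months.** Section 7.2 does say "Mobile phone numbers will be deleted after intermediate analysis", but these are the research team's copies. Each GP keeps a list with telephone numbers, completes the 9-month form, and is contacted by the research team to close follow-up (section 9.1). Keeping the team's numbers longer is unnecessary and would go against what patients are told in section 11.4.
- **The bias runs towards declaring the CPR safe.** Nothing in the protocol shows more losses or more deaths in the CPR arm. The calculations above assume one or the other.
- **Independent review would catch the problem.** It checks patients' condition at the end of follow-up, but only in a random 20% of cases (section 9.1).
- **Imputation methods may sit in an analysis plan that is not shown.** That is fair, and their absence is not part of this point.

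None of this supplies a definition of severe, a severity item or a place to record death. A GP who knows that a patient has died still has no field in which to say so.

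**Conclusion.** The point holds. As written, the severe-CHD endpoint in section 3.2 cannot be derived from the planned data, and section 6 and the Summary describe a different outcome. Death is omitted from the endpoints, the evaluation criteria and the form, in a trial that sets out to show uncompromised outcome. Last-resort exclusion may then remove some deaths from the comparison, and the 3-month harm check is the most exposed because it depends on interviewing the patient.

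These statements rest on the protocol text alone, since the follow-up form is printed in full. The size of any bias does not: the documents give no death rate, no severe-CHD rate and no expected loss by arm. The illustrations range from no bias to an almost complete masking of a true excess, depending on assumptions the protocol cannot settle. The defect is an endpoint that cannot be measured and a missing safety outcome, not a demonstrated bias in favour of the CPR.

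**What to change.** Before the forms are printed:

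- **Sections 3.2 and 6:** define severe CHD and use the same definition in both, in the synopsis and in the Summary.
- **Annex 3, 3- and 9-month forms:** add vital status with date and cause, and a dated CHD category (CHD death, infarction or unstable angina, revascularisation, stable CHD).
- **3-month follow-up:** obtain vital status from the GP when the patient cannot be reached.
- **Safety outcome:** count death in it.
- **Section 10.3:** replace extrapolation and exclusion with analysis of all enrolled patients in their allocated arm, and add a worst-case sensitivity analysis for the safety outcome. The imputation method can be left to the analysis plan.

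The cost is a few form fields, a GP query for patients not reached at 3 months, and modest extra analysis. The sample size and the confidentiality arrangements do not change. Vital status and severity would be hard to recover once 15,000 patients have been followed without these fields.

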### 3.3 Randomisation

Participating GPs will be split in two groups by simple randomisation, one using the cardiovascular CPR for each patient complaining of chest pain (intervention group) and the other working with usual clinical practice (control group). Randomisation will be performed with a table of random numbers by a member of the research team not involved in the current study and blinded to the identity of GPs.

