#### 4.4 Selection and recruitment procedure

Swiss GPs and physicians of the Department of Ambulatory Care and Community Medicine in Lausanne will be contacted and asked to participate the study. Starting from a defined date, each GP will enrol a defined number of patients reporting any type of chest pain, according to inclusion criteria.

Sampling of all the GPs recruited will be performed in order to assess characteristics of participants (age, place, type of practice) and minimize cohort effect. Investigators may decide to use pre-existing GPs network such as Sentinella, which can insure correct sampling of Swiss GPs.

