### 10.1 Number of subjects

Calculation of the number of subjects is based upon the TOPIC study, targeting the same population of patients with chest pain. We used a sample size calculation table for cluster-randomized trial to calculate the number of clusters needed with different values of subjects per cluster ( $m$  value). Calculation has been made for different variables up to the endpoints of the study. We chose the following variables for the calculation of the number of subjects: number of paraclinical tests, number of referral to specialist, number of hospitalisations.

[figure not shown]
All the true proportions for each variable in the control arm of the sample size calculation table come from the TOPIC study results. We then decided a reasonable decrease expected in the rate of paraclinical tests, referral and hospitalisations while using the CPR, which led us to the expected proportions in the intervention arm

In the TOPIC study, investigators reported 42% (284/672) of patients with paraclinical tests, 16% (110/672) with referral to specialist and 8% (53/672) hospitalised up to 12 months of follow-up (2).

To choose the number of cluster needed in each arm of the trial we took a coefficient of variation of 0.2. Final decision about number of subjects per cluster and number of clusters was based upon practical considerations so that recruitment procedure remains comfortable for GPs and to limit its duration.

Based upon the results shown above, we chose a number of 150 GPs in each arm, with 50 patients per cluster, so that the power of the study is sufficient to get a difference in paraclinical tests. We therefore need a total amount of 300 GPs, each of them recruiting 50 patients complaining of chest pain, leading us to a total amount of 15,000 patients.

Duration of inclusion is also calculated upon the TOPIC study in which chest pain occurred in 672 cases among 24,620 consultations during 300 weeks. We can therefore expect 2 to 3 patients with chest pain per week on the average, which leads us to an inclusion period of about 6 months for GPs to enrol the 50 patients needed.

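### Simple randomisation of GPs does not secure the 150 per arm of section 10.1 and leaves place and practice type to chance; restricted allocation would be a modest, cheap improvement once the unit of randomisation is settled

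*Protocol*

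**What the plan says.** On the method, section 3.3 states: "Participating GPs will be split in two groups by simple randomisation". On the tool it adds: "Randomisation will be performed with a table of random numbers by a member of the research team not involved in the current study". That person is also to be blinded to who the GPs are. No blocking, stratification, minimisation or fixed quota per arm is mentioned.

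On size, section 10.1 states: "we chose a number of 150 GPs in each arm, with 50 patients per cluster", and then: "We therefore need a total amount of 300 GPs, each of them recruiting 50 patients complaining of chest pain". Equal arms are therefore part of the stated design.

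On cluster characteristics, section 4.4 states: "Sampling of all the GPs recruited will be performed in order to assess characteristics of participants (age, place, type of practice". The same section approaches both Swiss GPs and physicians of a university ambulatory department. The Synopsis likewise lists private practices in Western Switzerland and that department. Section 3.3 makes no use of these characteristics.

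On the unit, sections 1.3 and 3.1 put randomisation and intervention at the level of the GP's office, whereas section 3.3 allocates GPs. Section 3.1 also requires that control GPs do not know of the prediction rule.

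**The concern.** Two things do not fit together. First, the sample size rests on a fixed, equal number of clusters per arm, while independent allocation from a random-number table gives a random number per arm. Second, the protocol collects place and type of practice for every recruited GP, yet leaves their balance to chance.

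The outcomes in question, tests and referrals, are decisions of the GP. If they differ by setting, an uneven split of settings acts through whole clusters of 50 patients. That settings do differ in this way is plausible but is an assumption: no section of the protocol says so.

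The allocation method has to be right before the first cluster is randomised. A later analysis plan can adjust for an imbalance but cannot change the allocation that produced it.

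**Working it through.** **Inputs from the protocol (section 10.1).** 300 GPs, 150 per arm, m = 50 patients per GP; control proportion with paraclinical tests p0 = 0.42 (284/672); for the variation between clusters, "we took a coefficient of variation of 0.2" (k = 0.2).

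**Assumed, because not in the readable text.** Two-sided alpha of 0.05, power of 80% or 90%, and the intervention proportion p1.

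**1. The plan's own figures.** 2 × 150 × 50 = 15,000, as stated. For the 150 per arm, the usual formula for unmatched clusters is

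c = 1 + (zα + zβ)² × [p0(1−p0)/m + p1(1−p1)/m + k²(p0² + p1²)] / (p0 − p1)².

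With p1 = 0.38 and 90% power: (1.960 + 1.282)² = 10.51; the bracket is 0.00487 + 0.00471 + 0.01283 = 0.02242; so c = 1 + 10.51 × 0.02242 / 0.0016 = 148.2, rounded up to 149. The stated 150 is therefore plausible, though it cannot be strictly reproduced. Solved the other way, 150 clusters per arm detect a difference of about 3.5 points (80% power) or 4.0 points (90% power).

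**2. Arm size under simple randomisation.** The number of GPs in one arm follows Binomial(300, 0.5), with SD = √300 / 2 = 8.7.

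- P(exactly 150/150) = 4.6%.
- 95% range 133 to 167 GPs, which at 50 each is 6,650 to 8,350 patients.
- P(140/160 or more uneven) = 27%; P(130/170 or more uneven) = 2.4%.

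**3. What that costs in power.** With v = p(1−p)/50 + 0.04p² for each arm,

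power = Φ( (p0 − p1) / √[v0/(c0 − 0.5) + v1/(c1 − 0.5)] − 1.96 ).

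| Design power at 150/150 | Power at 133/167, either arm smaller |
|---|---|
| 80.1% | 79.4% to 79.9% |
| 90.1% | 89.5% to 89.9% |

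The loss at the edge of the 95% range is under 1 percentage point.

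**4. What chance imbalance in a GP characteristic could do.** For a binary characteristic with prevalence q (assumed) and 150 GPs per arm, the SD of the difference in prevalence between arms is √[4q(1−q)/300]. Multiplying 1.96 SD by an assumed gap in test rate between GPs with and without the characteristic gives the 95% chance shift in the arm difference.

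| q | 95% difference in prevalence (points) | Shift, 10-point gap (points) | Shift, 20-point gap (points) |
|---|---|---|---|
| 10% | ±6.8 | ±0.7 | ±1.4 |
| 20% | ±9.1 | ±0.9 | ±1.8 |
| 30% | ±10.4 | ±1.0 | ±2.1 |
| 50% | ±11.3 | ±1.1 | ±2.3 |

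**5. Is this already budgeted?** k = 0.2 allows a between-GP SD of 0.2 × 42 = 8.4 points in the control arm. A binary characteristic contributes gap × √[q(1−q)]. A 10-point gap gives 3.0 points (q = 10%) to 5.0 points (q = 50%), well inside 8.4. A 20-point gap gives 6.0 points (q = 10%), 8.0 (q = 20%), 9.2 (q = 30%) and 10.0 (q = 50%), so the last two exceed what k allows. The largest 95% shift compatible with k = 0.2 is about 1.96 × 8.4 × √(4/300) = 1.9 points. Up to that limit the shift is already part of the planned standard error.

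**The case against.** Four objections deserve weight.

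- **The text may already mean equal arms.** Splitting GPs into two groups with a random-number table could mean drawing 150 from a complete list of 300. The figures in step 2 would then not apply. This stands as an ambiguity, but it is not what simple randomisation usually means, and section 3.3 would still need to say so.
- **Simple randomisation is legitimate with about 300 clusters.** This stands. Unequal arms cost almost nothing, and variation between GPs is budgeted through k. A reader might infer that the trial is underpowered or biased by its allocation; neither follows. Chance imbalance is random error, not systematic bias.
- **The effect of setting is not documented.** This also stands. A reader might infer that practice type and region are known to determine test and referral rates. The protocol gives no such data, and section 4.4 does not say what categories of place are meant. The analysis plan, which is not at hand, may also adjust for GP characteristics and so recover much of any lost precision.
- **Stratifying could do harm if the unit is not settled first.** Blocking individual physicians within the university department would place colleagues in both arms, although control GPs are not to know of the rule. If the department is a single unit, its physicians are not allocated independently, and the probability of an uneven split among them has no meaning. This objection stands in full and changes the remedy.

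**Conclusion.** The point holds in a limited form. Section 3.3, read in its usual sense, does not deliver the arm sizes fixed in section 10.1, and it makes no use of characteristics that section 4.4 already assesses. The mismatch in arm size is one of consistency: 4.6% chance of an exact split, 95% range 133 to 167, under 1 point of power.

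The balance argument is the better reason to change, and it is modest. Under an assumed 10-point gap between settings, chance would move the arm difference by up to about 0.7 to 1.1 points, and at most about 1.9 points is compatible with k = 0.2. The detectable difference is about 3.5 to 4.0 points. The gain is precision and credible balance on place and practice type.

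These figures assume independent 1:1 allocation of 300 GPs, two-sided alpha of 0.05, and the stated prevalences and gaps. If offices are the unit, there may be fewer clusters and the figures shift accordingly. This is a worthwhile refinement, not a flaw that threatens the trial.

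**What to change.** 1. **Settle the unit.** Make sections 1.3, 3.1 and 3.3 agree on office or GP, and keep physicians who share an office or department in the same arm. If offices are the unit, restate the target in section 10.1 in terms of offices, since 150 GPs per arm can then be met only approximately.
2. **Restrict the allocation.** In section 3.3, replace simple randomisation with computer-generated permuted-block allocation of those units, 1:1, stratified by a small number of categories of place. Add type of practice only where there are enough units; a department entering as one unit cannot form a stratum.
3. **Keep the allocator blinded.** Work from a coded list that carries only the stratum.
4. **Carry the strata into the comparison between arms.** State this in section 10.2 or in the analysis plan.

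The cost is a few sentences, the reconciliation of the unit and a little more work to set up the list. No extra patients are needed, and place and type of practice are already to be assessed; they only have to be known before allocation. The strata must stay few, because many small strata leave incomplete blocks and undo the balance.

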### 1.3 Study rationale

The study is a phase IV study and will take place in Swiss primary care settings. Target population are patients over 18 years consulting GPs and reporting any type of chest pain. We built a two arms trial to compare management of chest pain either in usual practice or aided by the cardiovascular CPR.

We chose a cluster randomized trial design and the intervention will be performed at the level of GP's offices. Randomization within the same health care unit and intervention performed at patient's level would have led to an important selection bias. This would have made impossible to guarantee an equivalent management of patients within the same arm as well as a strict distinction between the two arms.

GPs will therefore be enrolled in a prospective study and randomized either to use the Swiss CPR as an additional tool for the management of chest pain or go on with their usual practice. Each GP will have to include a defined number of patients complaining of chest pain.

Follow-up will concern number and type of paraclinical tests run by GPs, referrals and patient's outcome. We will also appreciate the use of the CPR, its acceptability and the satisfaction among the selected GPs. An intermediate analysis is planned during follow-up and stopping rules are defined in case of necessity.

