### 3.1 Overall description

This trial aims to assess implementation of a new cardiovascular CPR in primary health care. It is built as a prospective cohort study of primary care patients with chest pain. The cluster randomized trial design allows us to randomize GP's offices in two groups, one using the CPR in daily practice and the other working without, according to usual care practice. Thus, randomization and intervention are targeted at the level of GP's offices. Patient's outcome however is measured at the individual's level thanks to a case report form (CRF). Use of the CPR is measured directly by a few questions intended for GPs.

GPs selected to use the cardiovascular CPR will get intensive training to make as sure as possible that they use it in an equivalent way (see Annex 1 for description of GPs training). GPs of the usual practice group should not be aware of the CPR and will not get any information about it. In both groups, GPs will have to fill in a CRF for each patient complaining of chest pain.

Follow-up ends nine months after patient's index visit. An intermediate analysis is planned at three months. Members of research staff are designed to make sure that case report forms are complete for each patient and will get in touch with every agreeing patient at three months (intermediate analysis). GPs will assure the follow up until nine months (end of follow up) either by telephonic interviews or usual consultation. The research staff will control the follow up and remember GPs if necessary.

Independent physicians will review a defined randomized number of cases. They will control patient's condition at the end of the follow-up, validate the correct management of patients and verify the validity of the initial diagnosis of cardiogenic chest pain.

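### Section 3.1 makes the GP's office the unit of randomisation, but 3.3 randomises individual GPs and 10.1 counts GPs as clusters, so physicians sharing an office or department can land in opposite arms

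*Protocol*

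**What the plan says.** The protocol describes the unit of allocation in two ways.

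- **Office.** Section 1.3: "We chose a cluster randomized trial design and the intervention will be performed at the level of GP's offices". Section 3.1: "The cluster randomized trial design allows us to randomize GP's offices in two groups", and shortly after, "Thus, randomization and intervention are targeted at the level of GP's offices".
- **Individual GP.** Section 3.3, which sets out how allocation is done: "Participating GPs will be split in two groups by simple randomisation". It uses a random-number table, applied by someone who does not know who the GPs are. Section 10.1 follows the same unit: "we chose a number of 150 GPs in each arm, with 50 patients per cluster".

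Three further statements bear on the choice.

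- Section 4.4 recruits from at least one site with more than one physician: "Swiss GPs and physicians of the Department of Ambulatory Care and Community Medicine in Lausanne will be contacted".
- Section 3.1 requires that GPs in the usual-practice arm neither know of the prediction rule nor receive information about it.
- Annex 1 provides for training at the GP's own office.

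No section limits enrolment to one GP per office, and none says that physicians who work together are allocated together.

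**The concern.** If 3.3 is followed as written, two physicians at the same address are allocated independently. One may be trained in the score at that address while the other is meant to remain unaware of it. The score has only seven items taken from history and examination, so it passes easily between colleagues. Any uptake by control physicians makes the arms more alike.

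This affects both halves of the second objective. Dilution would hide a true reduction in investigations, and it would equally hide a true worsening of patient outcome. It could also feed the stopping rule in 3.4 that ends the trial when no difference is seen or expected.

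If 3.1 is followed instead, contamination within an office is avoided, but 10.1 then counts the wrong unit: 300 GPs are fewer than 300 offices wherever an office contributes more than one GP. One of the sections has to change under either reading, and contamination cannot be repaired in the analysis once allocation has been done.

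**Working it through.** **1. Do the sections agree?** Sections 1.3 and 3.1 say office; 3.3 and 10.1 say GP. The two coincide only if every office contributes exactly one GP. The protocol does not require this, and 4.4 contradicts it for the Lausanne department.

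**2. Chance that a site is split.** Under simple 1:1 randomisation of n physicians at one site, P(both arms present) = 1 − 2 × 0.5ⁿ.

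| Physicians at the site | P(split) |
|---|---|
| 1 | 0% |
| 2 | 50% |
| 3 | 75% |
| 5 | 94% |
| 10 | 99.8% |

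The protocol gives neither the number of GPs per private office nor the number of physicians joining from the department.

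**3. The plan's sample size.** 300 GPs × 50 patients = 15,000, which agrees with 10.1. The 150 per arm cannot be reproduced, because the expected intervention-arm rates and the power are not in the visible text.

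**4. Illustration of power.**

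- From 10.1: control rate p0 = 0.42 for paraclinical tests, m = 50 patients per cluster, c = 150 clusters per arm, coefficient of variation k = 0.2.
- Assumed: p1 = 0.38 and two-sided α = 0.05. The 38% was chosen because it comes close to the plan: with it the formula gives 148.2 clusters per arm for 90% power (111.0 for 80%).
- Formula: V = p0(1−p0)/m + p1(1−p1)/m + k²(p0² + p1²); power = Φ(|p0−p1|·√((c−1)/V) − 1.96).

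*As planned.* V = 0.004872 + 0.004712 + 0.012832 = 0.022416. Then 0.04 × √(149/0.022416) = 3.26, and power = Φ(1.30) = 90%.

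*GP-level allocation with leakage.* If a fraction f of the effect reaches the control arm as a whole, p0 becomes 0.42 − 0.04f.

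| f (assumed) | Control rate | Power |
|---|---|---|
| 5% | 0.418 | 87% |
| 10% | 0.416 | 84% |
| 20% | 0.412 | 75% |

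*Office-level allocation, two GPs per office (assumed).* There are then 75 offices per arm with m = 100.

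| k between offices | V | Power |
|---|---|---|
| 0.2 (colleagues vary as one) | 0.017624 | 74% |
| 0.2 × √0.75 = 0.173 (correlation 0.5) | 0.014416 | 82% |
| 0.2/√2 = 0.141 (colleagues independent) | 0.011208 | 90% |

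**5. Sensitivity to the assumed 38%.** With 39%, the unchanged plan has 68% power, and two GPs per office with k = 0.2 gives 49%. With 37% the figures are 98% and 90%.

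**The case against.** The strongest reply is that the protocol uses office and GP as synonyms: one GP, one office, one cluster. For solo practices that reconciles every section, and there is no contamination between colleagues. This stands for solo practices. It fails for the Lausanne department, and for any group practice that joins, because nothing excludes a second physician from the same office.

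A reader might also take section 1.3 as an outright ban on splitting a unit. It is not. The sentence reads "Randomization within the same health care unit and intervention performed at patient's level would have led to an important selection bias", so what it rejects is allocation of patients within a unit. The wish for a clear separation of the arms, expressed in the sentence after it, applies to physicians sharing a unit too, but it is a supporting argument only.

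On size, it is fair to object that no leakage figure comes from the documents, that solo GPs cannot be contaminated by office colleagues, and that the protocol does not say whether k = 0.2 describes GPs or offices. All of that stands, which is why the results are given as ranges. It is also true that simple randomisation will rarely give exactly 150 per arm, and that blocking or stratification could be added. Both are minor and form no part of this point.

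**Conclusion.** The contradiction is real, stands in the current text and is not resolved elsewhere in the protocol. Section 3.3 as written permits trained and control physicians in one unit, against the requirement in 3.1 that controls be unaware of the rule, and the resulting bias is towards no difference.

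Two stronger conclusions might be inferred and are not supported. The first is that colleagues will be split throughout the trial. The documents show only that they can be: a split is impossible in solo offices, of unknown frequency in private group practices, and near certain in the Lausanne department only if several of its physicians take part. The second is that the planned power is overstated by a known amount. No planned power is visible. The 74% for offices of two GPs is the bottom of a range reaching about 90%, and all power figures rest on the assumed 38%, the assumed α and the assumed leakage or office size.

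The finding does not depend on those figures. The unit of randomisation fixes the allocation list, the cluster count and the analysis, and it must be settled before allocation.

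**What to change.** - **Section 3.3:** state that whole offices are randomised, with all participating physicians of one office in the same arm and the Lausanne department treated as one such unit. The alternative is to enrol only one GP per office or department, which keeps 300 clusters.
- **Section 10.1:** count the same unit as the cluster, and restate the number of clusters, the cluster size, k and the power on it, with the expected number of GPs per office given. State whether k = 0.2 refers to variation between GPs or between offices.
- **If individual GPs are to remain the unit:** correct 1.3 and 3.1, say how control physicians in a shared office are kept unaware of the rule, and say how similarity between GPs of one office is handled.

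The cost is revised wording and a different allocation list. The person preparing the list can stay blind to identities by working from office codes. The downside is that the restated power may be less favourable, in which case more offices are needed or a lower power has to be accepted. The one-GP-per-office option avoids that but narrows the pool of eligible GPs.
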